CIS	carcinoma in situ
CNS	central nervous system
CTCAE	Common Terminology Criteria for Adverse Events
CTL	cytotoxic T lymphocyte
CVA21	coxsackievirus A21
DC	dendritic cell
DLT	dose-limiting toxicity
DSMC	Data Safety Monitoring Committee
ECG	electrocardiogram
ECOG	Eastern Cooperative Oncology Group
CRF	case report form
FAS	full analysis set
FDA	Food and Drug Administration
FFPE	formalin-fixed paraffin-embedded
GBM	glioblastoma multiforme
GFR	glomerular filtration rate
GM-CSF	granulocyte macrophage-colony stimulating factor
hCG	human chorionic gonadotropin
HR	heart rate
HSA	human serum albumin

IB	Investigator's Brochure
ICAM-1	intercellular adhesion molecule 1
ICF	informed consent form
ICH	International Council for Harmonisation
IFN	interferon
INR	international normalized ratio
IRES	internal ribosome entry site
GCP	Good Clinical Practice
MIBC	muscle invasive bladder cancer
MTD	maximum tolerated dose
NCI	National Cancer Institute
NMIBC	non-muscle invasive bladder cancer
ORR	overall response rate
PBS	phosphate buffered saline
PD-1	programmed cell death protein 1
PD-L1	programmed death-ligand 1
pfu	plaque-forming unit
PT	prothrombin time
PTT	partial thromboplastin time
RECIST	Response Evaluation Criteria in Solid Tumors
RFS	relapse free survival
SAE	serious adverse event
SAP	statistical analysis plan
SUSAR	Suspected Unexpected Serious Adverse Reaction
TCID ₅₀	50% tissue culture infective dose
TME	tumor microenvironment
TUR	transurethral resection
TURBT	transurethral resection of bladder tumor
UTI	urinary tract infection
WHO	World Health Organization

SYNOPSIS

Name of Sponsor/Company: Istari Oncology, Inc. Name of Investigational Product: PVSRIPO Name of Active Ingredient: PVSRIPO Protocol Number: LUMINOS-103 Phase: 1 Region: United States														
Title of Study: A Basket Trial Evaluating the Safety and Efficacy of PVSRIPO and PVSRIPO in Combination with Anti-PD-1/L1 Checkpoint Inhibitors in Patients with Advanced Solid Tumors														
Study center(s): Up to 5 centers														
Objectives and Endpoints: Objectives and endpoints described in the table below are in addition to those described in the master protocol (see Master Protocol Section 2 [Objectives and Endpoints]) and include those specific for Cohort E and F . Note that two cohorts of patients will be enrolled: Cohort E will include patients with recurrent non-muscle invasive bladder cancer (NMIBC) intended for transurethral resection of bladder tumor (TURBT) or cystectomy who will receive PVSRIPO via intravesical instillation and Cohort F will include patients with recurrent NMIBC intended for TURBT or cystectomy who will receive PVSRIPO via intravesical instillation after a sequence of 5% DDM and saline washes. Also note that the NMIBC substudy will NOT be treating patients with the combination of PVSRIPO and anti-programmed cell death protein-1/programmed death ligand-1 (PD-1/L1), i.e., Phase 2 will not be enrolled in the NMIBC substudy.														

  
 Objectives	Endpoints	
   
  Primary Objectives and Endpoints Phase 1 	
 
  Cohort E: To evaluate the safety and tolerability of PVSRIPO monotherapy administered by intravesical instillation to patients with recurrent NMIBC intended for TURBT or cystectomy. 	 Proportion of patients who undergo TURBT or cystectomy as scheduled. This endpoint replaces the master protocol endpoint described as “proportion of patients who received 1, 2 and 3 injections of PVSRIPO”. 	
 
  Cohort F: To evaluate the safety and tolerability of PVSRIPO monotherapy administered by intravesical instillation after a sequence of 5% DDM and saline washes to patients with recurrent NMIBC intended for TURBT or cystectomy. 	 Proportion of patients who undergo TURBT or cystectomy as scheduled. This endpoint replaces the master protocol endpoint described as “proportion of patients who received 1, 2 and 3 injections of PVSRIPO”. 	
 
  Secondary Objectives and Endpoints Phase 1 	
 
  Cohorts E and F: To assess the ability of PVSRIPO administered as monotherapy via intravesical instillation (Cohort E) or intravesical instillation after a sequence of 5% DDM and saline washes (Cohort F) to infect bladder cancer cells in patients with recurrent NMIBC intended for TURBT or cystectomy 	 Proportion of patients with evidence of PVSRIPO infection in resected tissues. This endpoint replaces the master protocol antitumor efficacy endpoints which include ORR, CBR, DOR, PFS and OS. 	
  
			Objectives	Endpoints	Primary Objectives and Endpoints Phase 1		Cohort E: To evaluate the safety and tolerability of PVSRIPO monotherapy administered by intravesical instillation to patients with recurrent NMIBC intended for TURBT or cystectomy.	Proportion of patients who undergo TURBT or cystectomy as scheduled. This endpoint replaces the master protocol endpoint described as “proportion of patients who received 1, 2 and 3 injections of PVSRIPO”.	Cohort F: To evaluate the safety and tolerability of PVSRIPO monotherapy administered by intravesical instillation after a sequence of 5% DDM and saline washes to patients with recurrent NMIBC intended for TURBT or cystectomy.	Proportion of patients who undergo TURBT or cystectomy as scheduled. This endpoint replaces the master protocol endpoint described as “proportion of patients who received 1, 2 and 3 injections of PVSRIPO”.	Secondary Objectives and Endpoints Phase 1		Cohorts E and F: To assess the ability of PVSRIPO administered as monotherapy via intravesical instillation (Cohort E) or intravesical instillation after a sequence of 5% DDM and saline washes (Cohort F) to infect bladder cancer cells in patients with recurrent NMIBC intended for TURBT or cystectomy	Proportion of patients with evidence of PVSRIPO infection in resected tissues. This endpoint replaces the master protocol antitumor efficacy endpoints which include ORR, CBR, DOR, PFS and OS.
Objectives	Endpoints													
Primary Objectives and Endpoints Phase 1														
Cohort E: To evaluate the safety and tolerability of PVSRIPO monotherapy administered by intravesical instillation to patients with recurrent NMIBC intended for TURBT or cystectomy.	Proportion of patients who undergo TURBT or cystectomy as scheduled. This endpoint replaces the master protocol endpoint described as “proportion of patients who received 1, 2 and 3 injections of PVSRIPO”.													
Cohort F: To evaluate the safety and tolerability of PVSRIPO monotherapy administered by intravesical instillation after a sequence of 5% DDM and saline washes to patients with recurrent NMIBC intended for TURBT or cystectomy.	Proportion of patients who undergo TURBT or cystectomy as scheduled. This endpoint replaces the master protocol endpoint described as “proportion of patients who received 1, 2 and 3 injections of PVSRIPO”.													
Secondary Objectives and Endpoints Phase 1														
Cohorts E and F: To assess the ability of PVSRIPO administered as monotherapy via intravesical instillation (Cohort E) or intravesical instillation after a sequence of 5% DDM and saline washes (Cohort F) to infect bladder cancer cells in patients with recurrent NMIBC intended for TURBT or cystectomy	Proportion of patients with evidence of PVSRIPO infection in resected tissues. This endpoint replaces the master protocol antitumor efficacy endpoints which include ORR, CBR, DOR, PFS and OS.													

Cohorts E and F: To assess viral shedding in urine of PVSRIPO administered as monotherapy via intravesical instillation (Cohort E) or intravesical instillation after a sequence of 5% DDM and saline washes (Cohort F) to patients with recurrent NMIBC intended for TURBT or cystectomy
	
PVSRIPO titers in urine

NMIBC=non-muscle-invasive bladder cancer; TURBT=transurethral resection of bladder tumor	
*Additional endpoints (e.g. adverse events [AEs], adverse events of special interest [AESI], etc.) can be found in master protocol.	

Study Design: The overall study design, including the dose limiting toxicity (DLT) definitions can be found in the master protocol (Master Protocol Section 3.1 [Overall Study Design]). This section focuses on those aspects of the study design specific to patients with recurrent NMIBC. Since the purpose of this substudy is to evaluate different methods of administration of PVSRIPO into tumors located within the bladder mucosa, the NMIBC substudy will NOT be treating patients with the combination of PVSRIPO and anti-PD-1/L1, i.e., Phase 2 will not be enrolled. Two cohorts of patients will be enrolled in this portion of the study. Both Cohort E and F will evaluate the administration of PVSRIPO monotherapy in patients with recurrent NMIBC intended for TURBT or cystectomy; patients enrolled in Cohort E will receive PVSRIPO via intravesical instillation while patients enrolled in Cohort F will receive PVSRIPO via intravesical instillation after a sequence of 5% DDM and saline washes. Cohort E: Because the dose for PVSRIPO administered by intravesical instillation has not been determined, Cohort E has been designed to evaluate 2 different dose levels of PVSRIPO using a 3+3 dose escalation approach (Figure 1). Three patients will initially be treated with a total dose of 2×10^9 50% tissue culture infectious dose (TCID₅₀) (Low Dose Cohort E) administered by intravesical instillation and the frequency of DLTs assessed. The decision to escalate/de-escalate the PVSRIPO dose will be based on the presence of DLTs observed during the 14 days following administration of PVSRIPO, in consultation with the independent Data Safety Monitoring Committee (DSMC). Provided that none of the initial 3 patients experience a DLT, the dose will be considered not to have exceeded the maximally tolerated dose (MTD) and the next cohort of patients (n=3) will receive a total dose of 1×10^{10} TCID₅₀ (High Dose Cohort E) via intravesical instillation. However, if 1 out of 3 patients enrolled in the Low Dose Cohort E experience a DLT, the cohort will be expanded by enrolling 3 additional patients. If no additional patient experiences a DLT, then the dose will be considered not to have exceeded the MTD and the next cohort of patients (n=3) will receive a total dose of 1×10^{10} TCID₅₀ (High Dose Cohort E) via intravesical instillation. In contrast, if a 2nd patient in the Low Dose Cohort E experiences a DLT during the initial enrollment of 3 patients--or expanded enrollment to 6 patients--then the maximum dose will have been exceeded, and the dose will be de-escalated to a total dose of 2×10^8 TCID₅₀ (Lowest Dose Cohort E). The evaluation of either the High Dose or Lowest Dose Cohort E will follow the same process as outlined above. Cohort F: Once enrollment in Cohort E has been completed, Cohort F will open to evaluate intravesical instillation of PVSRIPO after a sequence of 5% DDM and saline washes in patients (n=3) with recurrent NMIBC using the highest dose evaluated in Cohort E that does not exceed the maximum tolerated dose. The purpose of Cohort F is to assess if PVSRIPO infection of cells within the bladder mucosa is facilitated by pretreatment with a detergent able to disrupt the GAG layer of the epithelium.
	

Number of patients (planned): Approximately 3-12 patients will be enrolled in Cohort E and 3 patients will be enrolled in Cohort F.
	

Sample Size Justification:

The sample size for **Cohorts E** will be determined by the assessment of safety observed during the DLT period. It is expected that between 3 and 6 patients will be enrolled within each dosing cohort for a total sample size ranging from 6 to 12.

Diagnosis and main criteria for inclusion:

Eligibility criteria described in this section are in addition to those described in the master protocol ([Section 4 \[Study Population\] of the Master Protocol](#)) and are specific for **Cohort E and F**: patients with recurrent NMIBC intended for TURBT or cystectomy..

Inclusion Criteria

Patients are eligible to be included in the study only if all of the following criteria apply:

Both Cohorts:

1. Prior history of stage Ta, T1, or Tis urothelial carcinoma of the bladder.
 - a. Tumors with up to 50% squamous or glandular differentiation are eligible.
 - b. History of variant bladder histologies are excluded (e.g. sarcomatoid, plasmacytoid, small cell or neuroendocrine, pure squamous cell carcinoma, pure adenocarcinoma, micropapillary, nested, lymphepithelioma-like, clear cell)
2. Documented tumor recurrence at cystoscopy where the tumor is amenable to TURBT or cystectomy.
3. Measured or calculated (per institutional standard) creatinine clearance ≥ 45 ml/min (glomerular filtration rate [GFR] can also be used in place of creatinine clearance).
4. If the patient has an available formalin-fixed paraffin-embedded (FFPE) tumor specimen with an associated pathology report documenting NMIBC, the specimen must be confirmed to be available to send to the Sponsor. Patients **without** an available FFPE specimen are still eligible to enroll.
5. Measurable disease per Response Evaluation Criteria in Solid Tumors (RECIST) 1.1 is NOT required. This is an exception to the inclusion criterion outlined in the master protocol.

Exclusion Criteria

Patients are excluded from the study if any of the following criteria apply:

Both Cohorts:

1. Patients with exposure to intravesical agents (e.g. *Bacillus Calmette-Guérin* [BCG], mitomycin C, epirubicin, oncolytic viruses, anti-PD-1/L1 inhibitors, investigational therapies, etc.) within 3 months prior to the administration of PVSRIPO.
2. Patients whose anticoagulation or antiplatelet medications cannot be managed by local institutional guidelines to accommodate the safe intravesical instillation of PVSRIPO followed by TURBT, as determined by the treating physician.
3. Received prior radiation to the pelvis.
4. Received prior systemic therapy for bladder cancer, including PD-1/L1 inhibitors.
5. History of vesicoureteric reflux or an indwelling urinary stent.
6. History of stage T2 or higher bladder cancer
7. Medical conditions (as determined by the investigator) that would interfere with the ability of the patient to retain urine for 2 hours. Examples include urinary incontinence, overactive bladder, or low bladder compliance.

Investigational product, dosage, and mode of administration:

For **Cohort E**: PVSRIPO is a solution for intravesical instillation, formulated with 50 mM sodium phosphate in 0.9% sodium chloride, pH 7.4 with 0.2% human serum albumin (HSA) in phosphate buffered saline (PBS).

An initial dose of 2×10^9 TCID₅₀ will be administered to patients enrolled in **Low Dose Cohort E**. Depending upon the outcome of the DLT evaluation process as outlined in [Section 3](#) of this substudy, the dose will be either escalated to a total dose of 1×10^{10} TCID₅₀ (**High Dose Cohort E**) or de-escalated to a total dose of 2×10^8 TCID₅₀ (**Lowest Dose Cohort E**).

Each dose of PVSRIPO will be administered in a final volume of 60 ml by intravesical instillation; see the Pharmacy Manual for detailed instructions on how to prepare PVSRIPO for intravesical instillation. A urinary catheter will be inserted into the urethra under aseptic conditions according to local hospital protocol and the bladder drained completely. Using a catheter adapter with the syringe, the PVSRIPO suspension will then be instilled into the bladder via the catheter over a period of several minutes per local practice. After instillation the catheter will be removed, and the patient instructed to retain the instilled suspension in the bladder for a period of 2 hours. During this period, care should be taken to ensure that the instilled suspension has sufficient contact with the whole mucosal surface of the bladder. The patient should be encouraged to mobilize or, if lying down, to rotate between prone, supine, left lateral, and right lateral positions every 15 minutes.

After 2 hours the patient should void the instilled suspension directly into a toilet. After bladder evacuation, the next first voided urine sample should be collected for PVSRIPO Shedding.

The patient should be advised to limit their fluid intake for 4 hours prior to instillation and until bladder evacuation is permitted (i.e. 2 hours after instillation).

For **Cohort F**: Each patient will receive the following sequence of bladder washes prior to instillation of PVSRIPO: 100 ml saline followed by 75 ml 5% DDM followed by 100 ml saline. A urinary catheter will be inserted into the urethra under aseptic conditions according to local hospital protocol and the bladder drained completely. Using a catheter adapter with the syringe, each successive wash will be instilled over a period of several minutes per local practice. Each saline wash will be retained in the bladder for approximately 5 minutes and the 5% DDM wash will be retained within the bladder for 15 (± 5) minutes. At the end of each retention period, the bladder will be drained completely, and the next wash applied. Upon completion of the three washes, PVSRIPO will be instilled as described for Cohort E and in the Pharmacy manual. The process for pretreatment washes has been adapted from the process described for CG0070.

The dose administered to each patient enrolled in **Cohort F** will be the highest dose evaluated in Cohort E that does not exceed the maximum tolerated dose.

Reference therapy, dosage, and mode of administration: Not applicable.

Criteria for evaluation:**Efficacy:**

Since NMIBC is not routinely detected on imaging, it is not possible to assess responses to anti-cancer therapy using traditional oncology imaging endpoints like overall response rate (ORR). Therefore, histologic evaluation of surgical specimens after treatment is the most sensitive way to assess tumor response to PVSRIPO administration with a focus on quantifying the proportion of patients who have demonstrable infection of tumor tissue.

Safety: Safety will assess the frequency of DLTs observed during the 14 days following administration of PVSRIPO, evaluated by monitoring AEs, clinical laboratory test results

(hematology, clinical chemistry, and coagulation), vital sign measurements (blood pressure, heart rate [HR], and oral body temperature), and physical examination findings.

Statistical methods:

A statistical analysis plan (SAP) will be developed and finalized prior to the first planned database lock and will include more details related to the statistical analysis of this study's data.

Analysis Populations

The full analysis set (FAS) population includes all eligible patients who receive at least 1 dose of study drug. Analyses for the FAS population will be conducted based on the actual treatment received. Unless otherwise specified, the FAS population is the primary population for all efficacy and safety analyses.

Safety Analyses

Refer to the Master Protocol.

SCHEDULE OF ASSESSMENTS

The procedures and assessments to be performed for both **Cohort E and F** during the study are outlined in [Table 1](#). The timing and number of blood or urine samples collected for biomarker testing may be altered based on emerging data without requiring an amendment if the blood volume per day or overall does not increase and the patient is not required to have additional clinic visits or prolongation of a clinic visit, i.e., the risk-benefit profile for the patient does not worsen.

Study visits are outlined in the [Schedule of Assessments](#). Unscheduled assessments and visits to manage patient safety may occur at the Investigator's discretion. Study procedures performed at unscheduled visits should be recorded in the appropriate case report form (CRF).

Table 1: Schedule of Assessments: Cohort E and F

Protocol Activity	Screening Period	DLT Period			Day 30 (± 2 Days) ⁱ
		Cycle 1		End of Treatment	
	≤ 28 Days	Day 1	Day 2-5	Day 14 (+3 Days)	
Informed Consent ^a	X				
Polio Vaccine Booster	X				
Demographics	X				
Eligibility Evaluation	X				
Medical History, Surgical History, and Bladder Cancer History	X				
Complete Physical Examination	X	X			
Abbreviated Physical Examination			X	X	
Height (at Screening only)/Weight	X	X	X	X	
Vital Signs ^b	X	X	X	X	
ECOG Performance Status	X	X	X	X	
TriPLICATE 12 Lead ECG ^c	X				
Laboratory^d					
Hematology	X	X		X	
Clinical Chemistry	X	X		X	
Coagulation	X	X			
Urinalysis	X	X		X	
Serum or Urine Pregnancy Test (WOCBP)	X	X			
Study Treatment					
PVSRIPO intravesical instillation without washes (Cohort E) or with washes (Cohort F)		X			
TURBT or Cystectomy			X		
Tumor Assessments					
Images Obtained via Cystoscope ^e		X	X		
Other Samples					
Tumor Tissue Samples ^f	X (archival if available or optional pre-dose biopsy)		X (surgical specimen)		
PVSRIPO Shedding: Urine ^g		X (pre- and post-dose)	X	X	X
PVSRIPO Shedding: Stool ^h			X	X	X

Protocol Activity	Screening Period	DLT Period			Day 30 (± 2 Days) ⁱ
		Cycle 1		End of Treatment	
	≤ 28 Days	Day 1	Day 2-5	Day 14 (+3 Days)	
Blood Samples for Biomarker and Cytokine Analysis	X (serum prior to Polio Vaccine booster)	X (predose)	X	X	X
Other Clinical Assessments					
Adverse Events ^j		AEs up to 30 days post dose			
Concomitant Medication and Non-Drug Supportive Interventions		Con meds up to 30 days post dose			

AE=adverse event; Con meds=concomitant medications; DLT=dose-limiting toxicity; ECG=electrocardiogram; ECOG=Eastern Cooperative Oncology Group; TURBT=transurethral resection of bladder tumor; WOCB=women of childbearing potential.

^a Patient registration should be completed after all eligibility criteria are confirmed and as close to Cycle 1 Day 1 as possible.

^b Vital signs: includes temperature (oral, tympanic, or axillary), blood pressure, and pulse rate to be recorded in the sitting position after 5 minutes of rest.

^c Cardiologist review is not required for Screening ECG.

^d If the screening assessments are conducted within 3 calendar days prior to Cycle 1 Day 1, they do not need to be repeated.

^e Images to be obtained prior to instillation on the day of PVSRIPO intravesical instillation, and prior to surgical resection on the day of TURBT or cystectomy.

^f See [Section 6.3](#) for details regarding tissue biopsies.

^g All urine samples should be collected as described in the lab manual. On Cycle 1 Day 1, the pre-dose urine sample should be collected within 1 calendar day prior to PVSRIPO instillation. On Cycle 1 Day 1, the patient should void in the toilet after the 2-hour instillation and the next first voided urine sample should be collected for PVSRIPO Shedding. Urine samples should also be collected on Days 2, 4, 6, 8 and 14 of Cycle 1. If the day of the TURBT/cystectomy happens to coincide with a urine collection day, the urine sample should be collected prior to the surgery.

^h All stool samples should be collected as described in the lab manual.

ⁱ Refer to [Master Protocol Section 6.1](#) for details on adverse event reporting.

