3. INVESTIGATIONAL PLAN

The overall study design, including the dose limiting toxicity (DLT) definitions can be found in the master protocol ([Master Protocol Section 3.1 \[Overall Study Design\]](#)). This section focuses on those aspects of the study design specific to patients with recurrent NMIBC.

[figure not shown]
Since the purpose of this substudy is to evaluate different methods of administration of PVSRIPO into tumors located within the bladder mucosa, the NMIBC substudy will **NOT be treating patients with the combination of PVSRIPO and anti-PD-1/L1, i.e., Phase 2 will not be enrolled.**

Two cohorts of patients will be enrolled in this portion of the study. Both **Cohort E and F** will evaluate the administration of PVSRIPO monotherapy in patients with recurrent NMIBC intended for TURBT or cystectomy; patients enrolled in **Cohort E** will receive PVSRIPO via intravesical instillation while patients enrolled in **Cohort F** will receive PVSRIPO via intravesical instillation after a sequence of 5% DDM and saline washes.

Cohort E: Because the dose for PVSRIPO administered by intravesical instillation has not been determined, **Cohort E** has been designed to evaluate 2 different dose levels of PVSRIPO using a 3+3 dose escalation approach ([Figure 1](#)). Three patients will initially be treated with a total dose of 2×10^9 TCID₅₀ (**Low Dose Cohort E**) administered by intravesical instillation and the frequency of DLTs assessed. The decision to escalate/de-escalate the PVSRIPO dose will be based on the presence of DLTs observed during the 14 days following administration of PVSRIPO in consultation with the independent Data Safety Monitoring Committee (DSMC).

Provided that none of the initial 3 patients experience a DLT, the dose will be considered not to have exceeded the maximally tolerated dose (MTD) and the next cohort of patients (n=3) will receive a total dose of 1×10^{10} TCID₅₀ (**High Dose Cohort E**) via intravesical instillation.

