6.2.5. Clinical Safety Laboratory Assessments

Hematology, clinical chemistry, coagulation (international normalized ratio [INR], prothrombin time [PT], partial thromboplastin time [PTT], activated partial thromboplastin time [aPTT]), and urinalysis will be performed at the site's local certified laboratory per the schedule outlined in the Schedule of Assessments ([Table 1](#)). Additional tests may be performed at any time during the study as determined necessary by the Investigator or required by local regulations. A list of clinical laboratory tests to be performed is provided in [Table 5](#). Clinical chemistry, hematology, coagulation, and urinalysis results should be reviewed before dosing. Laboratory toxicities will be assessed using the National Cancer Institute (NCI) Common Terminology Criteria for Adverse Events (CTCAE), v5.0.

An abnormal laboratory value is not an AE unless it is considered to be clinically significant. Laboratory parameters for which clinically significant values are noted will be re-measured on the appropriate clinical follow-up arranged by the Investigator. Any laboratory value that remains abnormal at the end of the study and that is considered clinically significant should be followed according to accepted medical standards for up to 30 days or until the values return to normal or baseline or are no longer considered clinically significant by the Investigator. If such values do not return to normal/baseline within a period of time judged reasonable by the Investigator, the etiology should be identified, and the Medical Monitor notified.

If laboratory values from non-protocol specified laboratory assessments are performed at the institution's local laboratory as part of the monitoring of an SAE, then the results should be entered into the eCRF as part of safety reporting.

Table 5: Protocol-Specified Safety Laboratory Assessments

Laboratory Assessment	Parameters					
Hematology	Platelet Count	Hemoglobin				
	Complete Blood Count (CBC) with Differential (% and/or absolute values) for neutrophils, monocytes, and lymphocytes					
Clinical Chemistry	Blood Urea Nitrogen (BUN) or Urea	Serum Creatinine	Lactate Dehydrogenase	Albumin		
	Aspartate Aminotransferase (AST)	Alanine Aminotransferase (ALT)	Alkaline Phosphatase (ALP)	Total Bilirubin		
	Potassium	Sodium	Calcium	Chloride		
	Inorganic Phosphorous or Phosphate	Total Protein	Glucose (non-fasting)	Bicarbonate		

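### Coagulation is named as a DLT input but is never scheduled after dosing, and haematology and chemistry are scheduled only once, at Day 14 (+3)

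*Combined protocol and SAP*

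**What the plan says.** The Synopsis (Criteria for evaluation, Safety) states: "Safety will assess the frequency of DLTs observed during the 14 days following administration of PVSRIPO, evaluated by monitoring AEs, clinical laboratory test results". It names the panels in brackets, "hematology, clinical chemistry, and coagulation", and then adds vital signs and physical examination.

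Section 3 gives the use of these data: "The decision to escalate/de-escalate the PVSRIPO dose will be based on the presence of DLTs observed during the 14 days following administration of PVSRIPO". The Cohort F dose is then the highest Cohort E dose that does not exceed the maximum tolerated dose.

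In Table 1 the coagulation row reads "Coagulation X X", with the marks under Screening and Day 1. The other two rows read "Hematology X X X" and "Clinical Chemistry X X X", with the marks under Screening, Day 1 and Day 14 (+3). The Day 2-5 column contains surgery, vital signs, an abbreviated examination and a blood draw for biomarkers and cytokines, but no safety bloods.

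Section 6.2.5 sends the reader to Table 1 for the laboratory schedule and says: "Clinical chemistry, hematology, coagulation, and urinalysis results should be reviewed before dosing". Footnote d to Table 1 waives the repeat if the screening tests were done within 3 calendar days before Day 1.

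**The concern.** The plan names the evidence for judging DLTs, and its schedule does not deliver that evidence. For coagulation, a DLT assessment that follows the schedule has a baseline and nothing to compare with it. For haematology and chemistry it has one value near the end of the window, normally after an operation.

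The gap lies where the protocol itself expects activity. Section 3.1 justifies surgery at 2 to 5 days by a peak viral load within 5 days and innate immune effects that peak before 5 days. Section 1.2 lists bleeding among the risks and plans for anticoagulant and antiplatelet management, so coagulation is not an idle item on the list.

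What is at stake is the DLT count. It drives escalation in Cohort E, the dose used in Cohort F and one of the accrual-suspension rules in Section 6.4.

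**Working it through.** The plan states no figure to reproduce. The check is a column-by-column reading of Table 1 plus a count of days.

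**Is the Day 1 sample pre-dose?** Table 1 does not label it. Section 6.2.5 wants results reviewed before dosing, and footnote d lets a screening test up to 3 calendar days old take its place. Both make sense only for a baseline sample.

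**Scheduled samples per patient**

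| Panel | Screening | Day 1 (pre-dose) | Day 2-5 | Day 14 (+3) | Day 30 | Post-dose total |
|---|---|---|---|---|---|---|
| Coagulation | X | X | – | – | – | 0 |
| Haematology | X | X | – | X | – | 1 |
| Clinical chemistry | X | X | – | X | – | 1 |

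Rows with known timing support this reading of the columns: TURBT or cystectomy falls in Day 2-5, and the abbreviated examination in Day 2-5 and Day 14.

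**Time from dosing to the one post-dose sample.** Dosing is on Day 1 and the visit on Day 14 to 17: 14 − 1 = 13 days to 17 − 1 = 16 days.

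**Time from surgery to that sample, if surgery takes place as scheduled**
- Surgery on Day 2-5 (Table 1 column): 14 − 5 = 9 days to 17 − 2 = 15 days.
- Surgery 2 to 5 days after a Day 1 dose (Section 5.1.1.1), that is Day 3-6: 14 − 6 = 8 days to 17 − 3 = 14 days.

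On either reading the sample is post-operative, and no scheduled safety blood lies between dosing and surgery. Section 5.1.1.2 also permits immediate post-operative chemotherapy, a second competing explanation for an abnormal value at Day 14 (+3).

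**Visit window against DLT window.** Fourteen days after a Day 1 dose ends on Day 1 + 14 = Day 15, or on Day 14 if Day 1 is counted as the first day. The visit may be as late as Day 17, and Table 1 places it under the DLT Period. The two statements differ by two or three days at the edge.

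**What one event can do under the Section 3 rule**
- One true DLT among 3 patients, missed: 1/3 is read as 0/3, and the dose is escalated without the expansion to 6.
- Two true DLTs among 6, one missed: 2/6 is read as 1/6, and the dose is treated as not exceeding the maximum tolerated dose when it should have been treated as exceeding it.
- A surgical effect counted as a DLT in an otherwise clean group: 0/3 is read as 1/3, and 3 more patients are enrolled at that dose.

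**The case against.** The strongest reply is that laboratory values are one of four inputs. Adverse events are collected up to 30 days after dosing, and vital signs and an abbreviated examination are scheduled at Day 2-5 and Day 14. A reader might infer that DLTs are judged on laboratory results alone. The Synopsis does not say so. This limits the gap to toxicity that shows mainly in the laboratory, but does not close it.

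A reader might also infer that no post-dose coagulation value can exist, or that early toxicity cannot be seen. That goes too far. Unscheduled safety assessments are allowed and recorded, Section 6.2.5 permits additional tests at any time, and sites may take routine pre-operative bloods. But such testing is discretionary and usually follows suspicion, and nothing requires routine pre-operative results to be entered.

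Nor does the schedule establish that the Day 14 sample is always post-operative. The primary endpoint is whether surgery takes place as scheduled, so delay or cancellation is foreseen, and Section 5.1.1.1 gives 2 to 5 days only as the general timing. The confounding holds for patients operated on as scheduled.

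A reader might take the 14-day limit to exclude results from Day 16 or 17. Table 1 shows that visit inside the DLT Period, which points the other way. What remains is a wording mismatch.

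Two further objections stand. The DLT definitions are in Master Protocol Section 3.1, so it is not known here whether an asymptomatic laboratory value, or any coagulation value, can be a DLT. Section 6.2.5 adds that an abnormal value is an adverse event only if clinically significant. And the risks named in Section 1.2 are mainly local, with no systemic laboratory toxicity predicted.

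**Conclusion.** The point holds as a mismatch between the stated basis for DLT evaluation and the schedule, and it should be corrected. Per patient, the schedule gives 0 post-dose coagulation tests and 1 post-dose haematology and chemistry sample, 13 to 16 days after dosing. In patients operated on as scheduled, that sample comes 8 to 15 days after surgery across the two readings of surgical timing.

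Therefore a transient early laboratory abnormality would be found only by unscheduled testing, and a late one would be hard to separate from surgery or post-operative chemotherapy. With 3 to 6 patients per dose level, one missed or misattributed event is enough to change the escalation decision.

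The conclusion rests on two assumptions: that the Day 1 laboratory sample is pre-dose, which follows from Section 6.2.5 and footnote d, and that the master protocol allows some laboratory values to count as DLTs. If it does not, the safety-monitoring gap at Day 2-5 remains but the effect on escalation falls away, and the Synopsis wording is what needs to change. The documents do not show that a laboratory DLT is likely, and no probability of missing one can be calculated from them. The difference between the visit window and the DLT window is minor.

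**What to change.** 1. In Table 1, add haematology, chemistry and coagulation to the blood draw already scheduled at Day 2-5, taken before surgery. Alternatively, require the site's routine pre-operative results to be entered in the eCRF.
2. Add coagulation to the Day 14 (+3) draw. If coagulation is not intended as a DLT input, remove it from the Synopsis safety criteria instead.
3. Label the Day 1 safety laboratory samples as pre-dose in Table 1.
4. As a minor item, reconcile the Day 14 (+3) visit under the DLT Period with the 14-day window in the Synopsis and Section 3, and state whether results from that visit count in the DLT decision.

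The cost is an amendment to Table 1 and a few extra tubes at two draws that are already taken, with no new visit. Taking all additions, each patient has 3 extra panels at Day 2-5 and 1 at Day 14, so 4. With 6 to 12 patients in Cohort E (Section 7.1) and 3 in Cohort F, that is 9 × 4 = 36 to 15 × 4 = 60 local panels for the whole substudy. Capturing existing pre-operative results would cost less. A pre-operative sample does not resolve attribution after surgery, but it gives a post-dose value free of surgical effects to compare with the later one.
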